## 7.5 Secondary Outcome Measures

### 7.5.1 Safety

#### 7.5.1.1 Clinical Laboratory Parameters

The parameters of each clinical test will be presented for each group as n, mean, SD, median, minimum and maximum values at each scheduled assessment, as well as change from baseline. Baseline value will be the last value prior to dosing (SXC-2023/Placebo). Summary data (counts and % of patients) of clinically significant laboratory parameters and listings of all results will be presented.

#### 7.5.1.2 C-SSRS

A listing of the C-SSRS responses will be presented.

### 7.5.2 Pharmacokinetic Analyses

The following PK parameters will be determined for cocaine, BE, and SXC-2023 (as appropriate): maximum plasma concentration ( $C_{max}$ ), area under the concentration-time curve (AUC) from time 0 to time t ( $AUC_{0-t}$ ), AUC from time 0 to 12 hours post-dose ( $AUC_{0-12}$ ), AUC from time 0 to time infinity ( $AUC_{0-\infty}$ ), time to maximum plasma concentration ( $T_{max}$ ), trough plasma concentration ( $C_{trough}$ ), terminal rate constant ( $\lambda_z$ ), half-life ( $t_{1/2}$ ), clearance (CL) and clearance from plasma after oral administration (CL/F). Weight-adjusted parameters may be determined when necessary.

PK parameters will be calculated using noncompartmental analysis (NCA) implemented within a validated installation of Phoenix® WinNonlin®. Additional software may be used, if necessary. All softwares used will be documented in the PK section of the CSR.

#### 7.5.2.1 Plasma PK of Cocaine and BE

PK parameters for plasma cocaine and BE will be calculated as described in [Table 7-1](#) using noncompartmental methods. Plasma concentration-time profiles of cocaine and BE after infusion Sessions 3 and 5 will be analyzed to obtain PK parameter estimates and will be presented by participant and group summary statistics [N, mean, standard deviation (SD), % coefficient of variation (CV), median, minimum, maximum, geometric mean, CV% of geometric mean, and 90% confidence intervals (CI)]. Actual sampling times relative to the start of the cocaine infusion will be used in the NCA, where available, otherwise nominal sampling times will be used. Additionally, individual participant profiles will be plotted by day using actual times on linear and log-linear scales and mean profiles will be plotted by day using nominal sampling times on linear and log-linear scales.

#### 7.5.2.2 Plasma PK of SXC-2023

Plasma SXC-2023 concentration data for all participants in the PK concentration dataset will be summarized by day, treatment, and nominal sampling time, regardless of their inclusion in the PK analysis dataset. Summary statistics will include N, mean, standard deviation (SD), %

coefficient of variation (CV), median, minimum, maximum, geometric mean, and CV% of geometric mean. Individual participant and mean profiles of the concentration-time data will be plotted by day and treatment. Individual participant profiles will be plotted by day using actual times on linear and log-linear scales and mean profiles will be plotted by day using nominal sampling times on linear and log-linear scales.

PK parameters for plasma SXC-2023 will be calculated as described in [Table 7-1](#) using noncompartmental methods.

**Table 7-1 Pharmacokinetic Parameters**

Parameter	Description
For Plasma Cocaine and BE	
$C_{\max}$	Maximum observed plasma concentration
$T_{\max}$	Time of the maximum observed plasma concentration
$AUC_{\text{last}}$	Area under the plasma concentration-time curve from time 0 to the time of last quantifiable concentration ( $C_t$ ) calculated by the linear-up/log-down trapezoidal rule.
$AUC_{(0-11)}$	Area under the plasma concentration-time curve from time 0 to 11 hours post-dose calculated by the linear-up/log-down trapezoidal rule. Note: This parameter was not requested in the protocol but it will be reported because only subjects randomized to cocaine→saline will have a 12 hr. sample.
$AUC_{(0-12)}$	Area under the plasma concentration-time curve from time 0 to 12 hours post-dose calculated by the linear-up/log-down trapezoidal rule. This requires extrapolation for subjects randomized to saline→cocaine, for which the last timepoint is 11 hrs.
$AUC_{\text{inf}}$	Area under the plasma concentration-time curve from time 0 extrapolated to infinity. The terminal area from $C_t$ to infinity was calculated by using the approximation as $C_t/\lambda_z$ thus $AUC_{\text{inf}} = AUC_{\text{last}} + C_t/\lambda_z$
$AUC\%\text{extrap}$	Percent of $AUC_{\text{inf}}$ extrapolated from $C_t$ to infinity
$\lambda_z$	The terminal-phase exponential rate constant as calculated from the negative slope of the regression line for the terminal linear portion of the LN transformed plasma concentration versus time curve
$t_{1/2}$	The apparent terminal exponential half-life, calculated as $\ln(2)/\lambda_z$
CL	Total body clearance estimated as the drug dose divided by the plasma $AUC_{0-\text{inf}}$ (cocaine only)
$C_{\max}/70$	$C_{\max}$ for a 40 mg dose of cocaine normalized to 70 kg body weight ( $C_{\max} \times 70/\text{BW}$ )
$AUC_{0-11}/70$ and $AUC_{0-12}/70$	$AUC_{0-11}$ and $AUC_{0-12}$ for a 40 mg dose of cocaine normalized to 70 kg body weight ( $AUC_{0-11} \times 70/\text{BW}$ )
$AUC_{\text{inf}}/70$	$AUC_{\text{inf}}$ for a 40 mg dose of cocaine normalized to 70 kg body weight ( $AUC_{\text{inf}} \times 70/\text{BW}$ )

Parameter	Description
CL/70	Clearance for a 40 mg dose of cocaine normalized to 70 kg total body weight (cocaine only) ( $CL \times 70/BW$ )
For Plasma SXC-2023	
$C_{max}$	Maximum observed plasma concentration
$T_{max}$	Time of maximum observed plasma concentration
$AUC_{(0-24)} = AUC_{tau}$	Area under the plasma concentration-time curve from 0 to 24 hours post-dose. Note: the protocol requested $AUC_{(0-12)}$ but $AUC_{(0-24)}$ is more appropriate because SXC-2023 was dosed once per day.
$AUC_{inf}$	Area under the plasma concentration-time curve from time 0 extrapolated to infinity. The terminal area from $C_t$ to infinity is calculated by using the approximation as $C_t / \lambda_z$ thus $AUC_{inf} = AUC_{last} + C_t / \lambda_z$
$\lambda_z$	The terminal-phase exponential rate constant as calculated from the negative slope of the regression line for the terminal linear portion of the LN transformed plasma concentration versus time curve. A minimum of 3 time points are required to calculate $\lambda_z$ .
$t_{1/2}$	The apparent terminal exponential half-life, calculated as $\ln(2)/\lambda_z$
$C_{trough}$	Trough (predose) concentration
CL/F	Apparent oral clearance estimated as the drug dose divided by the plasma $AUC_{(0-24)}$ at steady-state (Day 9/10)
$C_{max}/70$	$C_{max}$ normalized to 70 mg body weight
$AUC_{(0-24)}/70$	$AUC_{(0-24)}$ normalized to 70 mg body weight
$AUC_{inf}/70$	$AUC_{inf}$ normalized to 70 kg body weight
CL/F/70	CL/F normalized to 70 kg body weight

PK parameters values will be listed for each participant in the PK analysis dataset by day and treatment, and the following descriptive statistics will be provided: N, arithmetic mean, SD, CV%, median, minimum, maximum, geometric mean and geometric CV% will be calculated for continuous PK parameters.  $T_{max}$  will be presented as median, minimum, and maximum.

### 7.5.2.3 Imputation of BLQ Values

For calculation of mean concentrations and generation of mean concentration versus time profiles, all BLQ values will be set to zero except when an individual BLQ value falls between 2 quantifiable values, in which case it will be treated as missing data.

For the PK analysis and individual concentration versus time plots, a concentration that is BLQ is assigned a value of zero if it occurs in a profile before the first measurable concentration. If a BLQ value occurs after a measurable concentration in a profile and is followed by a value above the lower limit of quantification, then the BLQ value is treated as missing data. If a BLQ value occurs at the end of the collection interval (after the last quantifiable concentration), it is treated as missing data. If 2 BLQ values occur in succession after  $C_{max}$ , the profile is deemed to have

terminated at the first BLQ value, and any subsequent concentrations are omitted from PK calculations.

In circumstances where alternative approaches to handling BLQ data are necessary, the relevant modifications will be appropriately documented in the clinical study report or final PK report.

#### **7.5.2.4 Imputation of Concentration at Dosing Time for AUC Calculation**

For all analytes, the last pre-dose concentration will be used as the concentration at the dosing time (i.e., at time =0).

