#### **2.2.2.3      Pharmacokinetics and Metabolism**

The distribution half-life of cocaine from an i.v. dose is about 10 minutes and the elimination half-life of cocaine was found to be about 1 hour (50-80 minutes) by Jeffcoat *et al.*, 1989, although subsequently a half-life of about 4 hours was reported by Cone (1995).

Cocaine is primarily metabolized by esterases in the plasma and liver to inactive metabolites, benzoylecgonine (BE), ecgonine methyl ester and ecgonine (Stewart *et al.*, 1977; Kloss *et al.*, 1984; Dean *et al.*, 1991; Kolbrich *et al.*, 2006). A very small portion of cocaine is metabolized by hepatic microsomal enzyme CYP3A to an active metabolite, norcocaine (N-demethyl metabolite) (Ladona *et al.*, 2000); however norcocaine is a minor metabolite that accounts for only 2 to 6% of the administered cocaine dose (Inaba *et al.*, 1978). In the presence of ethanol, liver carboxylesterase catalyzes the ethyl transesterification of cocaine to form cocaethylene plus methanol (Dean *et al.*, 1991).

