### 8.3 Cocaine

Cocaine hydrochloride solution, 20 mg/mL in 4 mL vial (*i.e.*, 80 mg/vial) is manufactured by Murty Pharmaceuticals Inc. (Lexington, KY) under a contract with NIDA. The cocaine hydrochloride solutions should be stored in a securely locked refrigerator within the pharmacy. Standard controlled substance procedures will govern access to the drug. Cocaine will be

administered by 2 ml i.v. push over 60 seconds by an investigator or qualified designee (such as a licensed registered nurse). Any unused drug will be disposed according to standard practices.

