### **5.2.2.1 Cocaine and BE**

Blood samples (4 mL) will be collected during infusion Sessions 3 (Day 2) and 5 (Day 9) at predose (approximately 15 minutes before the first infusion) and at 5, 15, 30, 65, 75, 90, 120, 150, and 180 minutes, and at 4, 8, and 12 hours after the first infusion. Samples will be collected for assessment of cocaine and BE PK in 4-mL Vacutainer™ tubes containing K2EDTA.

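### For i.v. push cocaine, the SAP joins the pre-dose value to the 5-minute sample by a straight line, so reported AUC is a few per cent low and CL a few per cent high; the treatment ratio is almost untouched.

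*SAP*

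**What the plan says.** SAP 7.5.2.4 fixes the starting concentration for every AUC: "For all analytes, the last pre-dose concentration will be used as the concentration at the dosing time". Four other statements decide what this does to cocaine.

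- **Input.** Protocol 8.3 has cocaine "administered by 2 ml i.v. push over 60 seconds".
- **Time origin.** SAP 7.5.2.1: "Actual sampling times relative to the start of the cocaine infusion will be used in the NCA".
- **Sampling.** SAP 5.2.2.1 takes cocaine samples "at predose (approximately 15 minutes before the first infusion) and at 5, 15, 30, 65, 75, 90, 120, 150, and 180 minutes", then at 4, 8 and 12 hours, all counted from the first infusion. When saline comes first, the 65-minute sample is 5 minutes after cocaine. Either way, nothing is drawn between the start of the push and 5 minutes.
- **Integration.** In SAP Table 7-1, AUC is "calculated by the linear-up/log-down trapezoidal rule". CL is "Total body clearance estimated as the drug dose divided by the plasma" AUC to infinity.

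Protocol Table 5 has the same trapezoidal rule, and the protocol gives no time-0 rule. Neither document provides an earlier sample, an end-of-push value or a back-extrapolated start.

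**The concern.** The time-0 rule suits oral SXC-2023 and the metabolite BE, both of which rise from their pre-dose level. Cocaine given as a one-minute push should peak at about one minute and then fall. Protocol 2.2.2.3 says: "The distribution half-life of cocaine from an i.v. dose is about 10 minutes". Because the 5-minute value exceeds the pre-dose value, linear-up applies, and the interval with the highest concentrations is integrated as a triangle.

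The affected outputs are the absolute cocaine AUC(0-11), AUC(0-12), AUClast, AUCinf and CL. SAP 7.5.2.1 presents these by participant and by group, and a reader may compare them with other studies. Their error would come from an integration convention, not from the data.

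**Working it through.** The plan states no figure for this, so there is nothing to reproduce. I integrated a known curve under the SAP rule and compared the result with its exact area.

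**Inputs from the documents.** One-minute input; distribution half-life 10 min; elimination half-life 50 to 80 min, or about 4 hours (both in Protocol 2.2.2.3); planned sampling times for both infusion orders; linear-up/log-down; tail Ct/λz, with λz from the last three points.

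**Assumptions.** A two-exponential curve; A/B of 0.5 to 4 (not in the documents); pre-dose cocaine of zero; all samples quantifiable; plasma level falling from the end of the push.

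**Formulas.** With α = ln 2/10, β = ln 2/(elimination half-life) and push length T = 1 min, each term with coefficient K and rate k is K(1 − e^(−kt))/(kT) during the push and K(e^(kT) − 1)e^(−kt)/(kT) after it. True AUCinf = A/α + B/β.

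**Worked case: 60 min, A = B = 1.**

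1. True AUCinf = 14.43 + 86.56 = 100.99. C(1) = 1.960, C(5) = 1.682, C(15) = 1.212.
2. True area from 0 to 5 min = 8.25, that is 4.9 × C(5).
3. SAP area from 0 to 5 min = ½ × 5 × 1.682 = 4.20. Loss = 4.04, about 49% of the segment and 4.0% of AUCinf.
4. The log rule on later, wider intervals slightly overstates a two-exponential curve and gives back about 0.7%. SAP AUCinf is 97.69 (cocaine first) or 97.60 (saline first): −3.3% or −3.4%. CL: 100.99/97.69 = 1.034 and 100.99/97.60 = 1.035, so +3.4% or +3.5%.
5. With a 1-min point: slope = ln(1.682/1.212)/10 = 0.03275 per min; imputed C(1) = 1.682 × e^(4 × 0.03275) = 1.917. Area = ½ × 1 × 1.917 + (1.917 − 1.682)/0.03275 = 0.96 + 7.19 = 8.15 (unrounded values used), against the true 8.25. AUCinf is 101.63 or 101.54: +0.6% or +0.5%.

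**Ranges over A/B 0.5 to 4 and both infusion orders.**

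| Elimination half-life | SAP rule: AUCinf | SAP rule: CL | With 1-min point: AUCinf | Back-extrapolated to time 0: AUCinf |
|---|---|---|---|---|
| 50–80 min | −2.1% to −6.5% | +2.1% to +7.0% | +0.3% to +1.4% | +0.9% to +3.3% |
| 240 min | −0.7% to −1.8% | +0.7% to +1.9% | +0.1% to +0.7% | +0.3% to +1.3% |

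Widening A/B to 0 to 5 gives −1.7% to −7.2% and −0.6% to −2.2% under the SAP rule. The sign never changes under this model.

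**Effect on the ratio.** If the arms have the same kinetics, the error is the same in both and a ratio of 1.00 stays 1.00. If SXC-2023 lengthened the elimination half-life from 65 to 80 min, the true ratio is (10·A/B + 80)/(10·A/B + 65):

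| A/B | True ratio | Under SAP rule |
|---|---|---|
| 0.5 | 85/70 = 1.214 | 1.220 |
| 1 | 90/75 = 1.200 | 1.207 |
| 4 | 120/105 = 1.143 | 1.152 |

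The shift is 0.006 to 0.009. For a larger true ratio of 1.25, with A/B from 0 to 5, the SAP rule reads 1.25 to 1.27.

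**Sample timing.** Moving the first sample within its ±1-minute window (4 to 6 min) moves the worked-case error from about −2.3% to −4.3%. With the 1-min point it stays between +0.5% and +0.7%.

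**The case against.** **The quoted rule is right at time 0.** The clock starts with the push, when no cocaine has entered, so the pre-dose value is correct there. This stands. The fault is the straight line across the unsampled 0 to 5 minutes, and the fix leaves the time-0 value alone.

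**The study question is comparative.** The cocaine PK objective asks whether SXC-2023 alters it. The rule is the same in both arms and on Days 2 and 9, and the ANCOVA adjusts for the baseline value. With 8 completers per group and an assumed residual log-SD of 0.15 to 0.30, the 95% CI around a ratio of 1 runs from about 0.85–1.18 to 0.72–1.39 (12 residual degrees of freedom). A shift of 0.01 is lost in that. This stands. A reader might infer that the rule could create or hide an interaction; the documents do not support that.

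**The size depends on the model.** A/B is assumed, the 4-hour half-life cuts the error to under 2%, and if sampled levels are still rising towards 5 minutes the bias is smaller. The proposed point was also tested on the same kind of curve that produced the error. All this stands, and is why a range is given.

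**An imputed point has a cost.** Protocol 12.7 and SAP section 7 rule out imputing missing data, although SAP 7.5.2.3 and 7.5.2.4 already assign values to concentrations. With an assumed 10% error per sample, the added point does not reduce scatter between profiles (SD 3.5% against 3.3%), so its benefit is less bias, not better precision. This stands, and the fix must state the exception.

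**Conclusion.** The point holds as a small, systematic error in the absolute cocaine AUC and CL. AUCinf is low by about 2.1% to 6.5% at elimination half-lives of 50 to 80 minutes and by 0.7% to 1.8% at 4 hours, with CL high to match. This rests on A/B of 0.5 to 4 and on decline from the end of the push.

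Three stronger readings fail. The time-0 value itself is not wrong. Cmax is not biased by the rule, because it is the observed maximum. The SXC-2023/placebo comparison is not materially biased: there is no shift when there is no effect, and about 0.01 otherwise (up to about 0.02 in the most extreme case run). BE and SXC-2023 are not affected. This is an improvement worth making, not a threat to the trial's conclusions.

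**What to change.** Amend SAP 7.5.2.4 for cocaine only:

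- Keep the pre-infusion value at time 0. Add a concentration at 1 minute (end of push) by log-linear back-extrapolation of the 5- and 15-minute post-cocaine samples. Integrate linearly from 0 to 1 minute and log-down afterwards.
- Use the added point for AUC and CL only, never for Cmax or Tmax.
- Name it as an exception to the no-imputation rule.
- If the 5- or 15-minute sample is missing, or the 15-minute value is not below the 5-minute value, apply the current rule and flag the profile.
- Leave BE and SXC-2023 as they are.

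Simple back-extrapolation to time 0 is the weaker choice: it ignores the one-minute input and overshoots by 0.9% to 3.3% at 50 to 80 minutes.

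The cost is a short SAP paragraph, an NCA setting and one model-based point per cocaine profile. Sampling and conduct do not change. If the sponsor prefers no imputed point, a caveat in the PK report giving the direction and likely size of the error is the minimum.

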#### **7.5.2.5 Significant Digits**

Concentration data and PK parameters will be generally reported to 3 significant figures. All associated summary statistics for these parameters will also be reported to 3 significant figures, except for N which will be reported as an integer. Discrete time parameters (such as Tmax and Tlast) and associated summary statistics will be reported to 2 decimal places.

### **7.5.3 Subjective Effects Analyses**

The VAS and BSCS analyses described below will be conducted on the Evaluable Population.

#### **7.5.3.1 VAS Responses**

Subjective effects VAS will be presented as summary statistics of maximum values, change from baseline and time to maximum values over 1-hour from the start of the cocaine infusion by treatment group for each question. Data will be compared between groups by Wilcoxon rank sum test. Additionally, within groups comparisons between study days will be done by Wilcoxon signed-rank test. Time to maximum VAS score will be analyzed using a Kaplan-Meier estimator. A log-rank test will be used to compare the time to maximum value by treatment groups (SXC-2023 vs Placebo). Comparisons will be considered statistically significant at a two-sided  $p < 0.05$ . The analyses for the 20mg and 40mg cocaine infusions will be performed separately.

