### **9.5 Infusion Session 2 (Day 1)**

The baseline infusion sessions (Sessions 2 and 3 – Study Days 1 and 2) provide cardiovascular effects, subjective responses, and PK data of cocaine in the absence of SXC-2023. During each baseline infusion session, each session will administer both cocaine and saline in a randomized order. Sessions 2 and 3 are randomized independently of one another. The participant's semi-supine blood pressure must be  $\leq 140$  mm Hg (systolic) and  $\leq 90$  mm Hg (diastolic), heart rate must be  $\leq 100$  beats per minute taken 15 and 30 minutes prior to the first cocaine infusion. If blood pressure or heart rate is elevated, it may be repeated one time to determine if the participant meets these criteria to receive an infusion. The participant's ECG taken in the half-hour (-30 minutes) prior to receiving any cocaine infusion must not have any clinically significant abnormal arrhythmia or interval changes. The pregnancy test must be negative before infusion.

The schedule of activities for infusion sessions are shown in [Table 4](#).

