## 4.2 Sample Size

Twenty participants will be randomized to 2 groups (10 for each group), receiving either SXC-2023 or placebo treatment for 7 days. Study participants who complete all five cocaine infusion sessions will be considered completed participants. This study requires 8 completed participants in each group. It is expected that, if 20 participants are randomized, there should be at least 8 completers in each group.

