#### 7.4.2 Cardiovascular Responses

Summary statistics (n, mean, standard deviation, median, minimum and maximum) of HR and BP by treatment, cocaine dose, infusion session, and timepoint will be presented. Maximum, maximum change and time to maximum from pre-infusion during the first hour after each infusion will be summarized by treatment, cocaine dose, and infusion session.

The maximum value and maximum change from pre-infusion values will be analyzed using an analysis of covariance (ANCOVA) model to compare the treatment groups (SXC-2023 versus placebo). The ANCOVA model will include the baseline (i.e., prior to SXC-2023/placebo treatment) maximum value or the baseline maximum change from pre-infusion as a covariate. The analyses for the 20mg and 40mg cocaine infusions will be performed separately. Effects will be considered statistically significant at a two-sided  $p < 0.05$ .

The distribution of the maximum value and maximum change for HR and BP will be explored. If not deemed normal or if right skewed, an ANCOVA analysis will be performed on the log-transformed HR and BP maximum value and maximum change. If the log-transformed data distribution is not normal then a Wilcoxon rank sum test will be used to compare treatment groups.

Time to maximum value will be analyzed using a Kaplan-Meier estimator. A log-rank test will be used to compare the time to maximum value by treatment groups (SXC-2023 vs Placebo). The analyses for the 20mg and 40mg cocaine infusions will be performed separately. Effects will be considered statistically significant at a two-sided  $p < 0.05$ .

ECG parameters extracted from Holter and their changes from pre-infusion (mean of the 3 pre-infusion ECGs) will be presented with summary statistics by visit and timepoint. Changes in ECG intervals during saline infusion as compared to those taken during cocaine infusions will be also reported as summary statistics. A listing of clinically significant ECG changes will be presented.

Pulse will be summarized by infusion session, timepoint, and treatment group.

Clinically significant ECG values will be presented in listings.

A listing of repeated assessments will be presented.

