### **7.5.3.2 BSCS Scores**

BSCS scores will be presented for each item as n, mean, SD, median, minimum, and maximum values at each scheduled assessment by treatment group. Group scores will be compared using Wilcoxon rank sum statistic for pre- and post- cocaine infusion assessments.

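### The between-arm tests of VAS maximum and BSCS do not adjust for each participant's own pre-treatment session, and the baseline for VAS change is undefined

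*SAP*

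**What the plan says.** **VAS (SAP 7.5.3.1).** The summaries are described as follows: "Subjective effects VAS will be presented as summary statistics of maximum values, change from baseline and time to maximum values over 1-hour". The between-arm test is then given: "Data will be compared between groups by Wilcoxon rank sum test". The earlier session clearly enters only within each arm: "within groups comparisons between study days will be done by Wilcoxon signed-rank test". Time to maximum has its own log-rank test. The significance level is two-sided 0.05, and the two cocaine doses are analysed separately.

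**BSCS (SAP 7.5.3.2).** "Group scores will be compared using Wilcoxon rank sum statistic for pre- and post- cocaine infusion assessments". No change score or covariate is mentioned.

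**Baseline sessions.** Protocol 9.5 says that Sessions 2 and 3 "provide cardiovascular effects, subjective responses, and PK data of cocaine in the absence of SXC-2023". Session 4 (Day 8) repeats the 20 mg dose of Session 2 (Day 1), and Session 5 (Day 9) repeats the 40 mg dose of Session 3 (Day 2), each in the participant's own earlier infusion order. SAP Table 4-5 schedules VAS and BSCS at the same times in all four sessions.

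**Analysis set.** VAS and BSCS are analysed in participants who completed all five sessions (SAP 6.4 and 7.5.3), so everyone analysed attended the matching baseline session.

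**Other endpoints.** For HR and BP, SAP 7.4.2 says: "The ANCOVA model will include the baseline (i.e., prior to SXC-2023/placebo treatment) maximum value or the baseline maximum change from pre-infusion as a covariate". SAP 7.5.2.6 uses the log of the baseline PK parameter as a covariate for cocaine and BE.

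**The concern.** Secondary objective 3 asks whether SXC-2023 alters the subjective effects of cocaine, which is a between-arm question. The signed-rank tests within each arm do not answer it. The test that does answer it, for VAS maximum and for BSCS, leaves stable differences between people in the error term, although the trial has measured each person's untreated response to the same dose.

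The treatment of endpoints is also uneven. The Protocol planned rank sum tests for HR/BP (12.4.2) and an ANOVA on treatment group for PK (12.5.2). The SAP moved both to baseline-adjusted models, but left the subjective endpoints close to the wording of Protocol 12.6 and gives no reason. Bounded or skewed ratings would explain avoiding ordinary ANCOVA. They would not explain leaving out the baseline, because ANCOVA on ranks can use it.

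At stake is the chance of detecting a real change in subjective effect with about 8 to 10 participants per arm.

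**Working it through.** **Inputs from the documents.** 10 randomized per arm and at least 8 completers per arm (SAP 4.2); two-sided 0.05 (SAP 7.5.3.1). No power, effect size, SD or between-session correlation is stated, so there is no planned power figure to reproduce.

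**Assumptions.** Bivariate normal scores with equal variance in both sessions; correlation r from 0 to 0.8; a treatment shift of 1.0 or 1.25 SD.

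**Step 1: variance of the arm difference, relative to using the Day 8 or Day 9 value alone.**
- Post-treatment value only: 1.
- Change from the earlier session: 2(1 − r). This gives 2.0, 1.4, 1.0, 0.6 and 0.4 at r = 0, 0.3, 0.5, 0.7 and 0.8.
- Ordinary ANCOVA on the earlier session: 1 − r². This gives 1.00, 0.91, 0.75, 0.51 and 0.36, before a small-sample penalty of 1 + 1/(2n − 4) = 1 + 1/12 = 1.083 at n = 8.

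A simple change score is therefore worse than the post value below r = 0.5, and no better than ANCOVA at any r before that penalty.

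**Step 2: simulated power at 8 per arm.**

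| r | Rank sum, 1.25 SD | Rank ANCOVA, 1.25 SD | Rank sum, 1.0 SD | Rank sum on change, 1.0 SD | Rank ANCOVA, 1.0 SD | ANCOVA, 1.0 SD |
|---|---|---|---|---|---|---|
| 0 | 62% | 60% | 44% | 25% | 42% | 43% |
| 0.3 | 62% | 63% | 44% | 34% | 45% | 47% |
| 0.5 | 62% | 70% | 44% | 43% | 50% | 54% |
| 0.7 | 62% | 82% | 44% | 65% | 64% | 71% |
| 0.8 | 62% | 90% | 44% | 82% | 75% | 85% |

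The power of rank sum on the post value does not depend on r. Under no effect, every method rejected about 5% of the time. At 10 per arm the pattern is the same: at r = 0.7 and 1.0 SD, 51% for rank sum and 82% for ordinary ANCOVA.

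**Step 3: adding infusion order to the rank ANCOVA (1.25 SD, no true order effect).** If the orders are balanced between arms, the term costs about 1 point or less. If they fall by chance, power is about 56%, 59%, 67%, 78% and 88% across the five values of r. The order term is thus better placed in a second model than in the main one.

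**Step 4: what baseline means for VAS change.** SAP 7.4.2 calls the within-session reference pre-infusion and uses baseline for the period before SXC-2023 or placebo. SAP Table 4-2 labels Sessions 2 and 3 as baseline. SAP 7.5.3.1 does not say which is meant. If the reference is the −30 minute score of the same session, the test does not use the earlier session. If it is Session 2 or 3, the test uses it through the change-score column above. VAS maximum and BSCS are unadjusted on either reading.

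**The case against.** The strongest case for the plan is that rank sum is valid and robust for bounded self-ratings, is the test named in Protocol 12.6, and serves secondary endpoints in a Phase 1 safety study without a power target. The HR/BP precedent is itself conditional: SAP 7.4.2 falls back to an unadjusted rank sum test if the log-transformed data are not normal. The benefit of adjustment rests on a correlation that nobody has stated. It may differ among nine VAS items that include depressed, anxious and bad effects. At r up to about 0.3 the gain is nil to slight, and an order term that is unbalanced by chance can turn it into a small loss. All of this stands, and it limits the point to efficiency and consistency.

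Three stronger readings are tempting, and the documents do not support them.
- *A chance imbalance in strong responders makes the planned test misleading.* Randomization keeps the test at its level, and chance imbalance is already covered by the 5%.
- *The VAS analysis ignores the baseline session altogether.* This is certain only for the VAS maximum. The change measure may already use Session 2 or 3.
- *Adjustment makes 8 per arm act like 8/(1 − r²), about 11 to 22 per arm for r = 0.5 to 0.8.* That formula describes ordinary ANCOVA before the small-sample penalty. It overstates the gain from ANCOVA on ranks at this sample size.

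**Conclusion.** The point holds in limited form. The between-arm tests of VAS maximum and BSCS leave out a matching pre-treatment measurement that the trial collects and that the SAP uses for HR/BP and PK. Whether the VAS change test uses it cannot be determined from the text.

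Under the 1.25 SD assumption at 8 per arm, rank ANCOVA loses about 2 points of power against rank sum at r = 0 (62% to 60%), gains about 8 at r = 0.5 (62% to 70%), 20 at r = 0.7 (62% to 82%) and 28 at r = 0.8 (62% to 90%). These figures rest on assumed normal data, an assumed effect and an assumed r; bounded or skewed scores could shift them. With little to lose at low r and a material gain from about 0.5, the change is worth making, but the planned test would not give a wrong answer.

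**What to change.** In SAP 7.5.3.1, define the VAS baseline: either the −30 minute score of the same session or the matching score from Session 2 or 3.

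In SAP 7.5.3.1 and 7.5.3.2, prespecify before unblinding a baseline-adjusted between-arm analysis, by ANCOVA or ANCOVA on ranks. Apply it to VAS maximum, VAS change and post-infusion BSCS, with treatment group and the matching earlier value as terms: Day 8 on Day 1 for 20 mg, Day 9 on Day 2 for 40 mg. Add infusion order as an optional second model, as SAP 7.5.2.6 does for PK. Keep the rank sum test as a sensitivity analysis.

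No new data are needed. The costs are one or two degrees of freedom, a small loss of power if r is near zero, no treatment estimate in VAS millimetres if ranks are used, and a documented departure from the test named in Protocol 12.6.
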